while doing sensory testing during the intervention, we will ask you to stand on force plates; this will only take about 2 minutes without any burden to you. Next, I will be completing a health screening form to check that you do not have any medical condition that would prevent you in participating in this research study". Just to make sure your handedness, I am also going to give you a simple questionnaire named Edinburgh Handedness Inventory (EDI) in which you tick the column that from which hand you do the activities written in questionnaire.

"Now, I am going to give you a consent form to get your written consent that you are ready to participate in this study.

Then the consent form will be given to the participant for his/her consent followed by health screening form and Edinburgh Handedness Inventory questionnaire and will be requested to fill the forms.

The participant will be again asked about any doubt that he/she may have before starting the method. If you wish to withdraw you will be free to withdraw from the study at any point. Then the participant will be asked or Karakia.

Participants (n = 27 older healthy adults) will attend two intervention sessions with two different conditions. Each participant will receive the two conditions in a randomised order.

During the first intervention session (day 1), introductions, the consent process, and familiarisation will be undertaken.

Following this, the process involves three steps for each of the two respective sessions:

Step 1: Setup,
Step 2: Outcome measures, and
Step 3: Intervention.

There will be at least 48 hours or 2-7 days gap between the two sessions i.e., the first session will be performed at day 1 and session 2 will be performed on the day 3.

Setup:

For setup, the staircase procedure will be used to setup the thresholds for somatosensory detection task (SSDT) measurements. This involves determining the sensory threshold. The sensory threshold will be termed "100%".

A simple example for determining sensory threshold is 5mA=100% sensory threshold, 4.5 mA= 90% sensory threshold, 5.5mA=110% sensory threshold)

Outcome Measures:

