5.1 DESIGN

Repeated measures crossover design. Each participant will receive each of the interventions, at least 48 hours apart within 2-7 days gap between the sessions, in a randomised order. The study is double blinded.

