5.3 EXCLUSION CRITERIA

- Diagnosed vestibular disorder or active BPPV
- Fallen more than twice in the past 6 months (Gaebler et al, 1993)
- Any diagnosed neurological impairment
- Medical conditions that are contraindicated with nGVS such as implants in head, neck, ankle or right foot, epilepsy, cardiac arrhythmias, unexplained recurring headaches, diabetic neuropathy (Thakral et al., 2013).
- Medical conditions that are cautioned with electrical peripheral stimulation of the foot such as metal implants in the area, skin lesions (Kuzyk & Schemitsch, 2009)
- Medical conditions that might affect the testing such as such as speech dysfunction, cognitive impairment
- Any allergic skin reaction to sticking plasters as a similar substance is used in the foot electrodes and to fix the nGVS electrodes

5.4 PRIMARY OUTCOME MEASURE:

- True positive rate (TPR): The electrical stimulation will be applied at 10% below threshold, i.e., at 90% sensory threshold for 30 times. The number of times the participant correctly identifies the stimuli will be scored out of total 30 number of trials (Bottini et al., 2013; Ferre et al., 2012; Ferrè et al., 2011; Ferre et al., 2013).

5.5 SECONDARY OUTCOME MEASURES:

- True negative rate (specificity): This will be the number of trials in which the participants received a catch (i.e., no stimulation), and said "NO". (Ferre et al., 2011).
- False positive rates: This will be the number of trials in which the participants received a catch and said, "YES".
- False negative rate: This will be the number of trials in which 110% stimulus is given and participants say 'no'.
- Perceptual sensitivity (d')
- Response bias (C)

[figure not shown]
Signal detection analysis (Macmillan et al, 1991) will be used to interpret the data for the SSDT task. That is a reason for the plan to measure three categories (as described above) according to the participant's responses.

- COP sway length will be obtained from VALD Performance Force decks dual force plate system.

5. Methodology

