7.2 ADVERSE EVENTS

Any adverse events will be recorded in an adverse event form and reported to [name] (primary supervisor) for appropriate follow up.

8. Follow-Up

When the study results have been interpreted, a summary of the study findings will be sent to the participants.

9. Data Management

Screening and consent forms will be kept in a locked filing office. After consent, participants will be given a unique participant code, and all subsequent data will be recorded against this code. Computer files will be saved in a folder on AUT's hard drive that is only accessible to [name], [name] and [name], and on a USB hard drive that will be stored in a locked cabinet in [name]'s office. Data collection sheets will be kept in a locked cabinet in [name]'s office.

10. Sample size calculation

Based on data collected in previous study conducted by the team on healthy young adults "Investigating the effects on nGVS on somatosensory perception in healthy adults, a sample size of 27 participants is required after seeing the normality and order effect.

11. Statistical analysis

The SSDT results will be analysed using Signal detection analysis (Macmillan et al., 1991). The number of HITS (number of stimulus-present trials in which participant will say 'YES'), FALSE ALARMS (number of stimulus-absent catch trials in which participants will say 'YES'), MISSES (number of stimulus-present trials in which participant will say 'NO') and CORRECT REJECTIONS (number of stimulus-absent catch trials in which participant said 'NO') will be considered.

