Further, a mixed between within subjects' analysis of variance (ANOVA) will be conducted to assess the impact of two different interventions (nGVS and sham) on the participant's scores of perceptual sensitivity d' and response bias (C) across three timepoints (Pre intervention, during intervention and post intervention). The normative check will be conducted using distribution before proceeding for ANOVA. A longitudinal analysis of covariance will be conducted to evaluate the primary null hypothesis that the true positive rate is equal across the two conditions. For this purpose, a linear mixed regression model will be constructed. The model will be estimated post-intervention outcomes while adjusting for the pre-intervention outcomes. To account for repeat measures from the same participants, the model estimation will be done as a participant-wise random intercept. The null hypothesis will be tested by statistically comparing the model-estimated post-intervention means using t-tests. The statistical significance level will be set at 0.05. These means and their differences will be reported along with their 95% confidence intervals

A statistical analysis will be carried out using SPSS software. Data from each outcome measure will be analysed using two-way repeated measures ANOVA and post hoc t-tests to explore main effects and interactions.

The mean difference of Sway path length parameter will be analysed.

12. Quality Assurance

The research assistant will be trained in the protocol (if required) by [name].

13. Recruitment

If all participants have not been recruited by six months, recruitment will be ceased, and data collection/analysis will continue with those already recruited.

14. Project Management

[name]	Responsible for overall management of the research including organising appointment and supervision of RAs, recruitment, scheduling sessions, data collection, data processing, and data analysis.
Research Assistant	Responsible for assisting with data collection in lab sessions and doing randomisation and delivering the interventions or control as required.
[name]	Supervising project (primary supervisor).
[name]	Supervising project (secondary supervisor). Overseeing data collection processes.
[name]	Supervising project (Advisor).

15. Screening

The Researcher will screen all potential participants using a screening form.

Forms attached separately.

16. Informed Consent

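### Section 11 gives two incompatible models for the secondary outcomes d' and C, and one of them, the mixed between-within ANOVA, does not fit a crossover

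*Protocol*

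**What the plan says.** Section 5.1 sets the design: "Repeated measures crossover design. Each participant will receive each of the interventions". The Method part of the synopsis agrees: "Each participant will receive the two conditions in a randomised order". Section 5.5 lists d' and C among the secondary outcomes.

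Section 11 then makes three statements about models:

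- For d' and C: "a mixed between within subjects' analysis of variance (ANOVA) will be conducted to assess the impact of two different interventions" (nGVS and sham), on "scores of perceptual sensitivity d' and response bias (C) across three timepoints (Pre intervention, during intervention and post intervention").
- For the true positive rate (TPR), the primary outcome: a linear mixed model of the post-intervention value, adjusted for the pre-intervention value, with a random intercept per participant.
- For everything: "Data from each outcome measure will be analysed using two-way repeated measures ANOVA and post hoc t-tests", covering main effects and interactions.

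The first and third statements both apply to d' and C.

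**The concern.** A mixed between-within ANOVA needs one factor that separates people and one that repeats within them. The sentence names two factors only. Time repeats within a person by construction, so the between factor can only be the intervention. In this trial the intervention also repeats within a person.

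Fitted that way, the model compares nGVS with sham as if different people had received them. Differences between people that cancel in a crossover stay in the error term. At stake are the standard errors and p-values for d' and C, the two outcomes that can separate better detection from a greater readiness to say yes. A missed shift in C could be read as absence of response bias beside a positive TPR result.

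Because the section also names a suitable model for the same outcomes, the analyst has two models that can give quite different p-values and no rule for choosing between them.

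**Working it through.** **Inputs from the protocol.** 27 participants (section 10), two conditions each, so 27 × 2 = 54 sessions; three timepoints per session; significance level 0.05 (section 11), taken as two-sided. The protocol gives no effect size, SD, power or within-person correlation, so the sample size cannot be reproduced and the correlation below is an assumption shown over a range.

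**Intervention main effect.** Let σ² be the variance of a person's session mean and ρ the correlation between that person's two session means.

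- Within-participant analysis: Var(difference) = 2σ²(1 − ρ)/27.
- Intervention as between factor: the model takes Var(difference) = 2σ²/27.
- Ratio of standard errors = 1/√(1 − ρ). For example, at ρ = 0.75 this is 1/√0.25 = 2.0.

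A paired t-test with n = 27 has 80% power for a mean difference of 0.56 SDs of the paired differences, which is 0.56 × √(2(1 − ρ)) in units of σ. Simulating that difference, and the null, under both tests gives:

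| Assumed ρ | SE inflation | True type I error, intervention as between factor | Power, intervention as between factor (paired test: 80%) |
|---|---|---|---|
| 0 | 1.0 | 5% | 81% |
| 0.3 | 1.2 | 2% | 70% |
| 0.5 | 1.4 | 0.7% | 53% |
| 0.6 | 1.6 | 0.3% | 41% |
| 0.75 | 2.0 | below 0.1% | 17% |

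The paired test holds about 5% type I error in every row.

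**Intervention-by-time interaction.** Let σ²_PT be the variance of each person's own time course that is common to both sessions, and σ²_e the residual.

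- Mixed between-within ANOVA: error variance σ²_PT + σ²_e, on 2 × (54 − 2) = 104 degrees of freedom.
- Two-way repeated measures ANOVA: error variance σ²_e, on 2 × (27 − 1) = 52 degrees of freedom.

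With σ²_PT = 0 (compound symmetry) the two error variances are equal and the mixed model loses nothing. The simulations below use a total variance of 1.0, a participant variance of 0.5, a session variance of 0.1 and a shift of 0.5 SD at the during and post timepoints:

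| σ²_PT | σ²_e | Error variance, mixed vs repeated measures | Power, mixed vs repeated measures |
|---|---|---|---|
| 0 | 0.4 | 0.4 vs 0.4 | about 54% vs 53% |
| 0.1 | 0.3 | 0.4 vs 0.3 | about 52% vs 65% |
| 0.2 | 0.2 | 0.4 vs 0.2 | about 50% vs 84% |

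The variance components are assumptions too; the protocol gives none.

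**The case against.** **The protocol already names a suitable model.** This stands. The repeated measures sentence covers d' and C and keeps the pairing. A reader might infer that the plan simply throws the pairing away; the document does not support that. What it supports is a conflict between two models, one of them unsuitable. The entry of 54 sessions as independent units is also an inference, since no data layout is described, but it is the only one that fits the factors named.

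**The main effect is the less relevant test.** This also stands. The pre value is taken before stimulation, so the main effect averages in a timepoint where nGVS cannot have acted, and the interaction mainly carries the effect. A reader might conclude from the main-effect figures that a real effect would probably be missed. That does not follow: the loss on the interaction runs from none to substantial, depending on a variance component that the protocol does not give.

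**The correlation may be low.** Possible. The sensory threshold is reset in each session, which removes some stable differences between people, and ten catch trials per assessment make d' and C noisy. Hence the range from 0 upward.

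**The wording might mean something harmless.** It could be loose language for a linear mixed model, or order of conditions could be the intended between factor. Neither fits well. The linear mixed model is described separately, for TPR. Order appears only in section 10, where "a sample size of 27 participants is required after seeing the normality and order effect", and it is not named as a factor in section 11.

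**This is a matter for the SAP.** Omitted detail would be. Here the protocol states an unsuitable model and contradicts it.

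**Conclusion.** The point holds as a contradiction in section 11 in which one of the two models for d' and C is wrong for the design. If that model is run, the loss on the intervention main effect goes from none at a correlation of 0 to a fall from 80% to about 17% power at 0.75. The loss on the interaction goes from none under compound symmetry to, for example, 65% down to 52% or 84% down to 50–51% when participants differ in time course. All of these figures rest on assumed correlations or variance components.

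Three limits apply. With positive correlation the error is conservative and does not create false positives. Only secondary outcomes are touched. The primary TPR model keeps the pairing through its participant random intercept. The wording is wrong as written, and the point is a should-fix, not a threat to the primary result.

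**What to change.** In section 11, delete the mixed between-within wording. State that d' and C are analysed with intervention (nGVS, sham) and time (pre, during, post) both as within-participant factors, using the two-way repeated measures ANOVA that the section already names, and say that this model governs.

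The random-intercept model planned for TPR would be an acceptable alternative for d' and C, but it is not needed to repair the defect. If order of conditions was meant as a between-participant factor, the section should say so.

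The cost is one sentence. No further data are needed, and the SPSS software already named in the protocol fits the model.

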6.1 SCHEDULE

Written consent will be obtained from the participants who were screened and met the study criteria during the first session (day 1), followed by intervention with either the nGVS or sham intervention. The participants will attend the second session 2-7 days later. The order of sessions one and two will be randomised according to a schedule determined by the researcher using www.randomization.com.

The same above mentioned procedure is done on :
 Session 1 (day 1, with intervention ngvs or sham) and repeated atleast 48 hours after on Session 2 (between day 2-7, with intervention sham or ngvs)

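### The primary model for this two-session crossover names no session (period) term, so any session shift left after baseline adjustment costs power or, with unequal orders, biases the nGVS-sham difference

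*Protocol*

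**What the plan says.** Section 5.1 defines the design: "Each participant will receive each of the interventions, at least 48 hours apart within 2-7 days gap between the sessions, in a randomised order". Section 6.1 covers the allocation of order: "The order of sessions one and two will be randomised according to a schedule determined by the researcher using www.randomization.com". It gives no block size.

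Section 11 sets the primary test: "A longitudinal analysis of covariance will be conducted to evaluate the primary null hypothesis that the true positive rate is equal across the two conditions". The model is then described as follows: "The model will be estimated post-intervention outcomes while adjusting for the pre-intervention outcomes". On the correlation between the two sessions it says: "To account for repeat measures from the same participants, the model estimation will be done as a participant-wise random intercept". The model-estimated means are compared by t-tests, and "The statistical significance level will be set at 0.05".

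Condition is therefore a fixed effect by implication, the pre-intervention value is a covariate, and participant is a random intercept. Session, period, order and sequence are not named. The ANOVAs in the same section use intervention and the three timepoints within a session (before, during, after), and no session factor either.

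Order appears in the statistical sections only once, in section 10: "a sample size of 27 participants is required after seeing the normality and order effect". That sentence is about the team's earlier study in young adults.

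**The concern.** In a two-period crossover, each participant's nGVS-minus-sham difference contains the treatment effect plus or minus the shift between sessions. The sign depends on which condition came first. A random intercept removes stable differences between people but not this shift.

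A shift is plausible here. The outcome comes from a yes/no detection task that is repeated in both sessions, and introductions, consent and familiarisation take place on day 1 only. If the model has no session term, the shift has two places to go. When the orders are nearly balanced it adds to the residual variance, so the test becomes conservative and loses power. When the orders are clearly unequal, part of it also enters the estimated treatment difference.

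**Working it through.** **Inputs from the protocol.** N = 27, two sessions, randomised order, alpha 0.05 (two-sided assumed). Because 27 is odd, 14:13 is the most even split possible.

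**The plan's own figure.** N = 27 cannot be reproduced, because section 10 gives no effect size, SD or power. Solving backwards with a two-sided paired t-test, N = 27 gives 80% power for a standardised paired effect of 0.56 and 90% power for 0.65. I use 0.56 as an assumption.

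**Set-up.** Let D be a participant's nGVS-minus-sham difference, in units of its SD. Let p be the session 2 minus session 1 shift that remains after baseline adjustment. Then D = effect + p if nGVS came second, and D = effect - p if nGVS came first. The protocol gives no value for p, so I take 0, 0.25 and 0.5.

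**Bias without a session term** = p x (n1 - n2)/N:
- 14:13: 1/27 = 3.7% of p, so 0.01 SD at p = 0.25 and 0.02 SD at p = 0.5.
- 17:10: 7/27 = 25.9% of p, so 0.06 SD at p = 0.25 and 0.13 SD at p = 0.5.

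**Standard error at 14:13, p = 0.5.** Without the term, the variance of D is about 1 + 0.25 x (1 - 1/729) x 27/26 = 1.26, so the SE is about 1.122/5.196 = 0.216. With the term, SE = 0.5 x sqrt(1/14 + 1/13) = 0.193. The simulated mean SEs are 0.214 and 0.191.

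**Simulation.** 60,000 trials per setting, paired analysis without session against the two-sequence analysis with session. Where two power values are given, they depend on which order has more people.

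| Split | p | Type I error without / with | Power without | Power with |
|---|---|---|---|---|
| 14:13 | 0 | 5% / 5% | 80% | 80% |
| 14:13 | 0.25 | 4.4% / 5% | 77% or 80% | 80% |
| 14:13 | 0.5 | 2.8% / 5% | 70% or 76% | 80% |
| 17:10 | 0 | 5% / 5% | 80% | 77% |
| 17:10 | 0.25 | about 5.5% / 5% | 67% or 86% | 77% |
| 17:10 | 0.5 | about 6.5% / 5% | 49% or 90% | 77% |

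Separate simulation runs differ by about one percentage point. The high power values at 17:10 are not a gain: they come from a bias that happens to favour the true effect.

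**How likely is imbalance?** If the list were simple randomisation (an assumption), the chance that the orders differ by 7 or more, i.e. 17:10 or worse, is 24.8% from Binomial(27, 0.5).

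**How much does the baseline absorb?** In a small illustrative mixed-model check at 18:9 (150 trials per scenario, assumed variances, frequent convergence warnings), a session shift of 0.10 in TPR left a bias of about 0.03 when it affected only the post-intervention value. The bias was about 0.01 when the shift affected pre and post equally. With the session term it was about 0 in both cases.

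**The case against.** The strongest reply is that the design already protects the comparison. The sensory threshold is set again in each session, TPR is scored at 90% of that threshold, and each session has its own pre-intervention measurement. Familiarisation comes before the first measurements, and the catch trials are disclosed only after session 2. This stands in part. A shift common to the whole session is partly recalibrated away, so it would be wrong to say that every session effect damages the analysis. What remains is the unabsorbed part of a common shift and any shift specific to the later measurements. No document gives its size.

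A second reply is that section 11 is a short narrative and an unseen SAP may add the term. That is possible. But the protocol sets out outcome, covariate, random effect and test for its primary model, and that description followed as written omits session. Block size is different: it may well be fixed elsewhere, so its absence is not counted as a fault.

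Three stronger readings are tempting and not supported:
- A reader might infer from section 10 that the plan contradicts itself, by recognising an order effect and then ignoring it. The remark concerns the earlier young-adult data and reports no result, so it neither shows that an effect is expected here nor justifies leaving the term out.
- A reader might infer that the primary test is invalid. Under simple randomisation, averaged over all possible splits, the estimate is unbiased and type I error is 5.0% at a shift of 0.5. The bias and the raised error rate are conditional on a chance imbalance.
- A reader might quote 70% as the power at 14:13. That is the unfavourable direction at the larger shift; the other direction gives 76%.

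**Conclusion.** The point holds in limited form. The primary model as described lacks a term that a two-period crossover analysis should carry. Near balance the harm is lost precision: 0 to 3 points of power at a residual shift of 0.25 SD and about 4 to 10 points at 0.5 SD, with a test that is conservative rather than liberal. At 17:10 it is a bias of 0.06 to 0.13 SD and a type I error of about 5.5 to 6.5%, given that split. These sizes rest on an assumed effect of 0.56 SD and an assumed residual shift; the protocol gives neither. The change should be made because it is cheap, not because serious bias has been shown.

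**What to change.** Add session (1 or 2) as a fixed effect to the primary mixed model in section 11. Analyse the secondary outcomes with a mixed model that also includes session. For these, the two-way repeated-measures ANOVA has to be replaced, which is more than adding one term.

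The cost in the primary model is one degree of freedom and no new data. If there is no session effect, power falls by 0 to 3 points: essentially none at 14:13, and from about 80% to 77% at 17:10.

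Optionally, state that the order list uses small permuted blocks, if this is not already fixed elsewhere. Blocks keep the split close to even but do not guarantee 14:13: a block size of 6 can end at 15:12, and section 13 lets recruitment stop at six months with fewer than 27 participants. The session term protects the comparison in either case.

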6.2.4 OUTCOME MEASUREMENT PROCESS THROUGH SOMATOSENSORY SIGNAL DETECTION TASK (SSDT)

This outcome measurement process involves carrying out a SSDT. The SSDT will be administered using a repeated-measure design before, during and after delivering each intervention (real nGVS or sham). During the SSDT, electrical stimuli will be delivered to the lateral border of the right foot through electrical stimulation (Digitimer, DS7A) to identify the threshold and -10% (Ferre et al., 2011). The different stimulus type trials which will be delivered to the right foot during the SSDT are A (above: 10% threshold, i.e., 110%), B (below: -10% threshold, i.e., 90%) and C (sham in which no stimulus will be present i.e., 0%). The trials will be delivered randomly to avoid any learning effect by the participant. Participants will report whether they can detect each trial. Through these measurements, we will determine the following outcome measures:

- True positive rate (TPR): The number of tactile stimuli a person can feel when stimulation is set at 90% sensory threshold.
- True negative rate: When a person receives a catch (no stimulation), they say “no”
- False positive rate: When a person receives a catch (no stimulation), they say “yes”
- False negative rate: When a person receives a 110% stimulus, they say “no”
- COP sway length in millimetres

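### The primary model's single baseline slope mixes between- and within-participant relations and can cost precision on the nGVS–sham contrast; splitting the baseline avoids this at little cost

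*Protocol*

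**What the plan says.** The design is a two-session crossover: "Repeated measures crossover design. Each participant will receive each of the interventions" (section 5.1). The primary outcome is TPR at 90% of sensory threshold: "The number of times the participant correctly identifies the stimuli will be scored out of total 30 number of trials" (section 5.4). Section 6.2.4 puts a baseline in every session: "The SSDT will be administered using a repeated-measure design before, during and after delivering each intervention (real nGVS or sham". The synopsis (Method) adds that "the process involves three steps for each of the two respective sessions", the first step being set-up, in which the sensory threshold is determined. The threshold is therefore re-set at each visit.

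Section 11 fixes the primary analysis: "A longitudinal analysis of covariance will be conducted to evaluate the primary null hypothesis that the true positive rate is equal across the two conditions", fitted as a linear mixed regression. On the covariate it says: "The model will be estimated post-intervention outcomes while adjusting for the pre-intervention outcomes". On the participant effect it says that "the model estimation will be done as a participant-wise random intercept". On the test: "The null hypothesis will be tested by statistically comparing the model-estimated post-intervention means using t-tests". Nothing in the protocol separates a participant's average baseline from the session-to-session difference in baseline, and section 11 names no period term.

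**The concern.** Because everyone receives both conditions, the adjusted treatment estimate is the mean post difference minus the slope times the mean pre difference. The only slope that belongs there is the within-participant one: how far a participant's post score moves when that participant's own pre score moves from one session to the other.

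A random-intercept model with one baseline covariate estimates a weighted mix of that slope and the slope between people. The between-person slope is often the steeper of the two, because stable differences between people appear in both pre and post scores. When baseline absorbs much of the between-person variance, the mix is pulled towards it. Multiplying a noisy pre difference by too steep a slope adds noise to the primary contrast. An adjustment meant to gain precision can then lose some, in a trial of 27 for which section 10 gives no effect size, SD or power.

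**Working it through.** **Inputs from the protocol.** 27 participants, two sessions each, TPR out of 30 trials, a baseline in each session, a participant random intercept, significance level 0.05. Section 10 gives nothing from which 27 could be reproduced, so there is no power figure to check against.

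**Assumed inputs.** Participant variance vb, session variance vs (shared by pre and post within a session) and occasion variance ve = 1. Pre and post each equal participant + session + occasion.

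**Slopes.**
- Within participant: w = vs/(vs + ve).
- Between participants (from session sums): (2vb + vs)/(2vb + vs + ve).

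**Variance using slope b, relative to the unadjusted paired difference:** 1 + b² − 2bw. This is smallest at b = w, where it equals 1 − w². The adjustment beats no adjustment only when b < 2w.

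**Numbers put in.** The fitted b is the mean slope from simulated REML fits of the stated model (4,000 runs per setting).

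| vb, vs | within | between | fitted b | formula | simulated, stated/unadjusted | simulated, stated/split |
|---|---|---|---|---|---|---|
| 4, 0 | 0 | 8/9 = 0.89 | 0.76 | 1 + 0.578 − 0 = 1.58 | 1.56 | 1.48 |
| 4, 1 | 0.50 | 9/10 = 0.90 | 0.81 | 1 + 0.656 − 0.810 = 0.85 | 0.85 | 1.08 |
| 4, 3 | 0.75 | 11/12 = 0.92 | 0.87 | 1 + 0.757 − 1.305 = 0.45 | 0.47 | 1.01 |

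The formula and the simulation agree. The fitted slope lies between the two true slopes, nearer the between-person one. The split model pays a small price for estimating its own slope: in the first row its variance is 1.56/1.48 = 1.05 times the unadjusted one.

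**TPR as Binomial(30), logit participant SD 0.4–1.2.** Variance under the stated model divided by variance under the split model, over several sets of runs:
- No session effect: 1.13 to 1.70.
- Session SD 0.3: 1.02 to 1.29. In the middle case (participant SD 0.8) it is 1.11 to 1.17, or about 1.15.
- Session SD 0.6: 0.97 to 1.09.
- Session SD 1.0: 0.97 to 0.98.

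With participant SD widened to 0.3–1.5, the range with no session effect is 1.04 to 1.75.

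**Against no baseline adjustment (same binomial model).** With no session effect the stated model was 1.08 to 1.80 times as variable (participant SD 0.3–1.5). At session SD 0.3 and participant SD 0.8–1.2 it was about 6–7% more variable. At session SD 0.4 the ratio was 0.75 to 1.00, and at 0.8 it was 0.36 to 0.43.

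**Validity.** Simulated type I error of the stated model was 0.046 to 0.064 across all settings.

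**Power.** Suppose that 27 participants give 80% power under the split model, which corresponds to a standardised paired effect of about 0.56. The effect is divided by the square root of the ratio, and power comes from the noncentral t.
- Ratio 1.11 to 1.16: 76% to 74%. At 1.15, 27/1.15 = 23.5 effective participants.
- Ratio 1.25: 71%, with 27/1.25 = 21.6 effective participants.
- Ratio 1.5: 63%, with 27/1.5 = 18 effective participants.

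**The case against.** **The single slope is inferred.** The protocol does not use those words, and a statistical analysis plan that is not shown could enter the covariate differently. It remains the plain reading, and section 11 fixes this model itself, so the point is about what the protocol states and not about a missing detail.

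**The large ratios need almost no shared session effect, which this design makes less likely.** The 90% intensity follows from a threshold found afresh at each visit, so calibration error moves that session's pre and post scores together. Section 6.2.3 uses 0.1 mA steps. At the synopsis's example threshold of 5 mA, one step is 0.1/5 = 2%, against a 10% offset. Assuming 1–2 logits per 10% of intensity, the stated/split ratio was 1.10–1.58 at 1% calibration error, 1.01–1.46 at 2%, 0.99–1.26 at 3% and 0.97–1.11 at 5%. Calibrating to each person's own threshold may also narrow the between-person spread. This stands as a reason to lead with the modest case. It does not remove the loss, since errors of one to three per cent still leave room for a material one.

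**A reader might infer that the primary test is biased or invalid.** The documents do not support that. Order is randomised, the estimate is unbiased, and the type I error stays near nominal.

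**A reader might also infer that differences between people wholly determine the slope, or that baseline should be dropped.** Neither follows. The slope is a weighted mix, and with moderate to large session effects the stated model is clearly better than no adjustment.

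**Conclusion.** The point holds as one of efficiency. As written, section 11 can give away precision on the primary contrast. The likely size is modest: a variance ratio of about 1.0–1.3 with a shared session SD of 0.3 on the logit scale, with a middle case near 1.15. It can reach about 1.7 if sessions share nothing beyond the participant, and it vanishes when the session effect is large. All these ratios rest on assumed variance components. The power figures also rest on an assumed 80%, so they show no stated figure to be wrong. The change is worth making because the gain and the cost are so unequal, and because it does not require knowing which variance scenario applies.

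**What to change.** In section 11, replace the single pre-intervention covariate with two terms: the participant's mean pre-intervention TPR over both sessions, and the session's deviation from that mean. Keep the participant random intercept. The nGVS–sham contrast is then adjusted by the within-participant slope only. Use the same form for TPR during stimulation if that outcome is analysed with this model. Make the change before outcome data are seen.

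The cost is one extra model term and one sentence, with no new data. The worst simulated penalty was about 2–3% more variance, when session effects are large.
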